12.10.1. Adverse events

All AE will be classified using MedDRA including Lowest Level Terms (LLT), Preferred Terms (PT) and System Organ Class (SOC).

TEAEs defined as AEs occurring after the start of the 1st study drug administration will be analysed. Other AEs will only be listed.

The absolute number of TEAEs as well as the number of patients with at least one TEAE will be tabulated by SOC and PT. Patients with SAEs, drug-related AEs will be analysed by SOC and PT.

The duration of the TEAE and the time between the last administration of study drug and the onset of the TEAE will be calculated.

TAAEs will be analysed by patients and infusions.

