3.2. Handling of Missing Data and Outliers

Regarding the primary criterion, a patient will be also considered as a non-responder if the patient is withdrawn due to lack of efficacy of the treatment (insufficient response to the investigational medicinal product [IMP]). In all other cases, if the INCAT score at EOS visit is missing, then the Last Observation Carried Forward (LOCF) approach will be applied and the last available adjusted INCAT disability score will replace the missing value at EOS visit.

The LOCF approach will also be used to handle the missing data of the secondary endpoint for adjusted INCAT and response at week 12 only.

When AEs are documented in the diary, dates of AE onset may be missing and as a result, TAAE cannot be defined. For AEs with a missing or incomplete start date, the response to the question “Did the AE start within 72 hours of an infusion” will be used for determining if the AE is temporally related to the infusion.

Partial dates of first symptoms and partial dates of diagnosis will be imputed by 15 if only the day is unknown and by 1st July if day and month are unknown. No imputation will be done if the year is unknown.

For the calculation of duration of AEs, partial start and end dates will be imputed with the first and last possible date within the period defined by the partial date, respectively. In general, no

calculation of duration will be made if either the start date or stop date is missing, i.e., cannot be imputed using pre-determined rules. No other general rules for the replacement of missing data are planned.

Data listings will always show the original CRF reported values and not the imputed values.

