- TEAEs by Action taken with IMP (None / Dose reduced / Dose increased / Discontinuation of IMP / Temporary interruption of IMP, (the action could also be a decrease of infusion flow rate))
- TEAEs by outcome (Resolved without sequelae / Resolved with sequelae / Not recovered / Recovering / Fatal / Unknown)
- Other significant AEs

A similar summary table will be produced for TAAEs as well as drug-related TEAEs and Serious TEAEs.

All TEAEs, SAEs, TAAEs and drug-related AEs will be summarized by SOC and PT, showing number of TEAEs, and number and percentage of patients with at least one TEAE, sorted by decreasing incidence of SOC and PT within SOC in the column “overall”.

Summary of TEAEs will also be presented by relevant subgroups (e.g., by age group [<65 years and ≥ 65 years], sex, race [white, non-white and unknown], and BMI [<30 kg/m² and ≥ 30 kg/m²]).

The rate of TEAEs by patient, course, infusion and drug-related AEs by course will be presented and sorted by decreasing incidence of PT in the column “overall”. Rate is defined as the number of events for unique PTs divided by the total number of patients, courses and infusions respectively.

Duration of most-common (those which occurred in at least 10% of the patients in the overall safety population) drug-related AEs will be calculated as is outlined in Section [5.7.2](#) and will be presented with descriptive statistics on recovered AEs (i.e., AEs with an outcome of “Recovered without sequelae” or “Recovered with sequelae”). Statistical unit of analysis will be the individual who recovered from drug-related AE. No imputation will be performed for the purposes of computing duration.

The time between the stop time of the last administration of IMP (before the onset of event) to the onset of the drug-related AEs will be calculated (in days) as is outlined in Section [5.7.2](#) and will be presented with descriptive statistics using the individual drug-related AE as statistical unit.

All Serious TEAEs, drug-related AEs, AEs leading to dose changes (action taken is not missing, “None” or “Not-applicable”) or discontinuation of IMP, and other significant TEAEs will be listed. These listings will include the event duration as well as the time elapsed (in days as is outlined in Section [5.7.2](#)) between the stop time of the last administration to the onset of the event.

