5.7.2. Safety

Adverse Event Duration

The duration of AEs will be calculated as:

$$\text{AE Duration (days)} = \text{AE stop date} - \text{AE start date} + 1$$

Similar formula will be used for any duration-related calculations.

Time to AE onset

The time to onset of an AE since the previous infusion will be calculated as:

$$\text{Time to AE onset (days)} = \text{AE start date} - \text{Date of previous IMP infusion} + 1$$

Similar formula will be used for any time to event-related calculations.

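### The duration summary for common drug-related AEs covers recovered events only, so it understates duration if any such event stays unresolved, and the number left out per preferred term is not shown

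*SAP*

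**What the plan says.** The SAP's duration summary (4.7.2) is built from these rules:

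- Scope: "Duration of most-common (those which occurred in at least 10% of the patients in the overall safety population) drug-related AEs".
- Population: it "will be presented with descriptive statistics on recovered AEs (i.e., AEs with an outcome of “Recovered without sequelae” or “Recovered with sequelae".
- Unit: "Statistical unit of analysis will be the individual who recovered from drug-related AE".
- Missing dates: "No imputation will be performed for the purposes of computing duration".

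SAP 5.7.2 computes duration as stop date minus start date plus one day. SAP 3.2 adds that, in general, no "calculation of duration will be made if either the start date or stop date is missing". An ongoing event therefore has no duration in any table or listing.

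Protocol 12.10.1 is broader: "The duration of the TEAE and the time between the last administration of study drug and the onset of the TEAE will be calculated". It restricts neither the outcome nor the commonness of the event. SAP 4.10.2, which records safety changes from the protocol, covers only the timing of vital signs and the added haemolysis analysis.

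SAP 4.7.2 also tabulates TEAEs by outcome, including the unresolved and fatal categories, repeats that table for drug-related TEAEs, and lists all drug-related AEs.

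**The concern.** Entry to the summary depends on the quantity being summarised. The resulting mean, median, quartiles and maximum describe how long reactions lasted among those that ended. A reader will want to know how long the drug's common reactions last, and the two answers differ as soon as one reaction fails to resolve.

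The denominators can be small. Ten per cent of the planned 42 patients is 4.2, so a preferred term qualifies with 5 patients. If each has one event, a single unresolved event is 1/5 = 20% of that term. The outcome table counts drug-related events in aggregate, so someone reading one term's median duration could not see how many events had been removed from it.

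**Working it through.** The plan states no figure for AE duration or for the share unresolved, so there is nothing to reproduce. The check follows the rules and then gives an illustrative range.

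**1. Which events enter.** SAP 4.7.2 has six outcome categories. The two recovered ones enter. Unknown, recovering, not recovered and fatal stay out.

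**2. When follow-up ends.** Protocol 9.5.3 stops follow-up at the final study visit only for unrelated events. Related events are followed as long as needed, or until they stabilise or the patient is lost, with a resolution date if they resolve. A related event can therefore close unresolved, but the end-of-study (EOS) visit is not its cut-off.

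**3. Direction.** Let T be the true duration and C the time from onset to last follow-up, with C unrelated to T. An event of length t enters with probability P(C ≥ t), which cannot rise as t grows. The recovered-only distribution is therefore shifted towards short durations, or is unchanged if all events resolve.

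**4. Size with one common cut-off (assumed).** Take exponential T and unresolved share u.

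- Median ratio = −ln(1 − (1−u)/2) / ln 2
- Mean ratio = (1 − u + u ln u) / (1 − u)

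| u | Median ratio | Mean ratio | Shortfall, median / mean |
|---|---|---|---|
| 0.05 | 0.930 | 0.842 | 7% / 16% |
| 0.10 | 0.862 | 0.744 | 14% / 26% |
| 0.20 | 0.737 | 0.598 | 26% / 40% |

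**5. Size with staggered onset (assumed).** Place onset one day after the start of each of 8 courses at 3-week intervals: days 1, 22, …, 148. As a worst case, stop follow-up at day 168. With t the days left and S = exp(−t/m) for mean duration m, the recovered-only mean is Σ[m − (t+m)S] / Σ[1 − S]. For mixtures, the terms are weighted.

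| Assumed durations (days) | True mean | Unresolved | Recovered-only mean | Relative bias (before rounding) |
|---|---|---|---|---|
| exponential, mean 3 | 3.00 | <0.1% | 3.00 | −0.1% |
| exponential, mean 7 | 7.00 | 0.8% | 6.84 | −2.3% |
| exponential, mean 14 | 14.00 | 3.9% | 12.96 | −7.5% |
| exponential, mean 30 | 30.00 | 12.7% | 24.17 | −19.4% |
| exponential, mean 60 | 60.00 | 28.5% | 36.41 | −39.3% |
| 95% mean 3, 5% mean 90 | 7.35 | 2.0% | 4.20 | −42.9% |

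At the same unresolved share, the common cut-off overstates the bias for exponential durations: its formula gives −13%, −30% and −50% at 3.9%, 12.7% and 28.5%. The mixture row shows that a small long-lasting subgroup can matter even when few events are unresolved.

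**6. How outcome is coded.** SAP 4.7.2 sets an AE's outcome to the maximum over its follow-up records, with recovering and not recovered ranked above both recovered categories. Read literally, an event recorded as not recovered and later as recovered is analysed as not recovered, and leaves the summary despite having an end date. The documents do not say whether follow-up records carry such interim outcomes.

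**7. Partial dates.** SAP 3.2 says: "For the calculation of duration of AEs, partial start and end dates will be imputed with the first and last possible date". SAP 4.7.2 says that nothing is imputed for duration. The two need reconciling, because any revised table depends on these dates.

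**The case against.** The case for leaving the plan alone has four parts.

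- **Nothing is hidden.** The SAP states openly that the statistics are on recovered AEs, and unresolved events appear in the drug-related outcome table and the listings. A reader might infer that unresolved reactions vanish from the safety report; the documents do not support that. What is missing is the count per preferred term beside the duration statistics.
- **EOS is not the cut-off.** A reader might infer that every event open at the EOS visit is dropped. Protocol 9.5.3 contradicts this for drug-related events, which are the only ones in this table. One that resolves later can enter if its outcome and date are captured.
- **The protocol is not specific.** It says only that duration will be calculated, sets no rule for ongoing events, and in 12.2 leaves technical detail to the SAP. This makes the departure mild. It does not remove it: the SAP narrows an unrestricted plan by relatedness, commonness and outcome, and 4.10.2 is where that should be recorded.
- **A Kaplan-Meier analysis has its own problems.** Patients may have the same reaction after several courses, so an event-level interval that ignores clustering would be too narrow. With about 5 patients the median may not be estimable. Both points stand and shape the fix.

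**Conclusion.** The point holds in conditional form. The summary selects on the outcome it measures, and it understates duration if any common drug-related event is unresolved at its last follow-up. It would go too far to say that the reported durations are biased short: the bias from this source is zero if all such events resolve, and the documents do not say how many will. The percentages above are illustrations resting on assumed exponential durations and assumed cut-offs, and the staggered case also assumes the worst-case stop at EOS. They run from negligible for short reactions to large for long or mixed ones.

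This is a minor matter in a descriptive safety display. No hypothesis test depends on it and the primary analysis is unaffected.

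**What to change.** In SAP 4.7.2:

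- Show the number of unresolved events per preferred term beside each duration summary.
- Add a Kaplan-Meier median time to resolution. Censor ongoing events at the last AE follow-up date, not automatically at EOS, and treat fatal events as never resolved.
- Define resolution by a recorded end date with ongoing set to No, instead of by the worst outcome across follow-ups.
- Use one event per patient per term, chosen by a stated rule, or a patient-clustered confidence interval.
- Settle whether partial dates are imputed for duration, so that 3.2 and 4.7.2 agree.

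In SAP 4.10.2, record the restriction relative to protocol 12.10.1.

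The cost is some SAP wording and one revised table; start, end and ongoing fields are already in the AE data. For terms seen in about 5 patients, the median or its interval may not be estimable. There, report the recovered-only statistics with the unresolved count. Because follow-up may stop when an event stabilises, censoring at last follow-up may itself be informative, which is a further reason to show the count.

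### The SAP gives two unreconciled partial-date rules for adverse event duration, and its time-to-onset formula does not measure the interval that its text defines

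*SAP*

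**What the plan says.** **Duration.** SAP 3.2, the general section on missing data, states: "For the calculation of duration of AEs, partial start and end dates will be imputed with the first and last possible date" allowed by the partial date. It adds that duration is generally left uncomputed only when one of the two dates is absent and the rules cannot supply it. SAP 4.7.2 then describes one summary: "Duration of most-common (those which occurred in at least 10% of the patients in the overall safety population) drug-related AEs will be calculated", restricted to events with a recovered outcome. That paragraph ends: "No imputation will be performed for the purposes of computing duration". The same section asks for listings of serious, drug-related, dose-changing or discontinuing, and other significant events, and says "These listings will include the event duration as well as the time elapsed" since the last administration. Under "The duration of AEs will be calculated as", SAP 5.7.2 gives stop date minus start date plus 1, with no rule for partial dates.

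**Time to onset.** SAP 4.7.2 defines the interval as "The time between the stop time of the last administration of IMP (before the onset of event) to the onset of the drug-related AEs", in days, and refers to 5.7.2 for the calculation. The 5.7.2 formula is the event's start date minus the date of the previous infusion, plus 1. Protocol 12.10.1 asks for the time between last administration and onset and gives no formula.

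SAP 4.10, on changes from the protocol, mentions neither matter.

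**The concern.** On duration, a programmer working from 3.2 computes a value for an event with a partial date; one working from 4.7.2 does not. The SAP does not say which section governs, or that 4.7.2 is a local exception. The 3.2 rule is also not neutral: pairing the earliest start with the latest end can only lengthen an event.

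On onset, the text names a clock interval that begins at the end of infusion, whereas the formula uses neither the stop time nor the onset time and counts the infusion day as day 1. Adding 1 is usual for an inclusive duration, where the first and last days both count. It is not how elapsed time is measured.

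Safety is the trial's secondary objective, and the duration and latency of drug-related events are planned outputs under it. The latency matters most within the first 72 hours after infusion, the window used to define temporally associated events. A reader could therefore see an event flagged as within 72 hours beside an onset of 4 days.

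**Working it through.** The plan has no figure to reproduce here. The check sets the rules side by side and applies them to invented dates.

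**1. Duration of an event with a partial date.** Formula (SAP 5.7.2): stop date − start date + 1.

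| Recorded start | Recorded end | SAP 3.2 | SAP 4.7.2 |
|---|---|---|---|
| 10 March | March, day unknown | 31 − 10 + 1 = 22 days | not computed |
| March, day unknown | 12 March | 12 − 1 + 1 = 12 days | not computed |
| March, day unknown | March, day unknown | 31 − 1 + 1 = 31 days | not computed |

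The last row is the extreme for two dates known only to the same month: 28 to 31 days, depending on the month, even if the event lasted one day.

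**2. Where the two rules meet.** The no-imputation sentence closes the paragraph on common, recovered, drug-related events. The listings cover all drug-related events, so they include these same events, and no local rule on imputation is given for them. If 4.7.2 is an exception for the summary and 3.2 governs the rest, the first event above is listed at 22 days and is absent from the summary.

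**3. Time to onset.** Let D be the number of calendar days from the infusion date to the onset date. Let a be the clock time of infusion stop and b the clock time of onset, each as a fraction of a day from 0 up to but not including 1. Assume that the infusion starts and stops on the same date.

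- Interval defined in the 4.7.2 text: D + b − a
- Formula in 5.7.2: D + 1
- Excess over the calendar-date difference: (D + 1) − D = 1 day, always
- Excess over true elapsed time: (D + 1) − (D + b − a) = 1 + a − b, which lies strictly between 0 and 2 days

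| Infusion stop | Onset | Elapsed (days) | Formula (days) | Excess (days) |
|---|---|---|---|---|
| 10 March 16:00 | 10 March 18:00 | 2/24 = 0.08 | 0 + 1 = 1 | 0.92 |
| 10 March 16:00 | 11 March 09:00 | 17/24 = 0.71 | 1 + 1 = 2 | 1.29 |
| 10 March 16:00 | 11 March 16:00 | 24/24 = 1.00 | 1 + 1 = 2 | 1.00 |
| 10 March 16:00 | 13 March 16:00 | 72/24 = 3.00 | 3 + 1 = 4 | 1.00 |
| 10 March 00:01 | 10 March 23:59 | 0.999 | 0 + 1 = 1 | 0.001 |
| 10 March 23:59 | 11 March 00:01 | 0.001 | 1 + 1 = 2 | 1.999 |

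No event after an infusion can have an onset below 1 day.

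**4. What depends on these quantities.** SAP 4.7.2 derives treatment-emergent status from onset dates, date-times and the investigator's timing assessment. It takes temporally associated status from the eCRF item on schedule. Neither uses the 5.7.2 onset formula.

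**The case against.** The best defence on duration is that a specific rule overrides a general one. Section 3.2 speaks of adverse event durations at large, while the 4.7.2 sentence closes one paragraph about one summary. This is a natural reading, and it stands as a possibility. It means that a reader who infers that the two rules simply exclude each other, or that the summary of common drug-related events will be biased upward, goes further than the text: for that summary 4.7.2 switches imputation off. What remains is that the SAP never states the exception, and that under it the listings and the summary disagree. Section 3.2 also says that listings show the values reported in the CRF rather than imputed ones. That settles how dates are displayed; it does not settle a derived duration printed beside them.

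On frequency, the diary asks for start and end dates and times and is checked at visits (Protocol 8.2.1, 10.2), so two month-only dates should be uncommon. But 3.2 itself expects missing onset dates from the diary, and neither document says how many partial dates there will be.

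On onset, 4.7.2 points to 5.7.2 and the formula there is explicit, so programmers will not diverge. Calling the infusion day day 1 is a stated convention applied alike to all events. That is fair as to reproducibility. It does not reconcile the formula with the interval that the text defines.

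A plain subtraction of stop time also has a gap. For an event during an infusion it is negative if that infusion's stop is used, and before the end of the first infusion no earlier stop exists. This objection stands, and the fix must provide for it.

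**Conclusion.** The point holds as a minor inconsistency in the SAP, with two parts.

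- **Duration.** The partial-date rules in 3.2 and 4.7.2 are not reconciled. Where 3.2 is applied, the duration is the longest that the partial dates allow (22, 12 and 31 days in the examples); where 4.7.2 is applied, there is none. The upward bias is conditional on 3.2 being used.
- **Onset.** The 5.7.2 formula overstates the calendar-date difference by exactly 1 day, and the elapsed time defined in 4.7.2 by just above 0 to just under 2 days. An onset at exactly 72 hours reads as 4 days.

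Two stronger readings are not supported. A reader might infer that every onset is one day too long; that is true only against the date difference, since the excess over elapsed time varies with the clock times. A reader might also infer that events near 72 hours are misclassified; they are not, because treatment-emergent and temporally associated status are derived otherwise. The effect is confined to descriptive safety tables and listings, and efficacy is not touched.

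The conclusion assumes infusions that do not cross midnight. It also assumes that the 5.7.2 sentence extending similar formulas to other time-to-event calculations is confined to safety, the heading under which it stands.

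**What to change.** 1. **One duration rule.** Apply no imputation, as in 4.7.2, to every adverse event duration output, both summaries and listings, and amend 3.2 to match. Report the number of events whose duration cannot be computed. The plus 1 in the duration formula can stay. Declaring 4.7.2 an exception to 3.2 would be a smaller edit, but the same event could still have a listed duration and no summarised one.
2. **Onset formula.** In 5.7.2, define time to onset as onset date-time minus infusion stop date-time. Where a time is missing, use the date difference without the plus 1, and report how many events rely on this fallback, since it mixes whole days with fractions of a day.
3. **Events during an infusion.** Report them as a separate category, outside the onset-time statistics.

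The data are largely planned already. SAP 4.7.2 works with event date-times, Protocol 6.1.3 records the date and time of administration in the eCRF, and SAP 4.7.1 summarises infusion duration in minutes, so a stop time should be derivable.

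The cost is SAP wording and programming. The downside is that events with partial dates drop out of the duration summary and have no duration in the listings; the documents do not give their number.

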3.1.4. Treatment

Patients who meet all the eligibility criteria will receive one dose of study drug at 2 g/kg over 2 to 5 days. Three (3) weeks later, they will start to receive 7 doses of study drug at 1 g/kg over 1 to 2 day(s) each, every 3 weeks (+/- 7 days).

Investigators or Study Nurses will call patients 4 days (+/-1 day) after the end of each study treatment course to document potential AEs and TAAEs (see Section [8.2.4](#)).

Duration of the treatment period will be approximately 21 weeks.

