- TEAE = “Yes” if AE onset date = start date of first IMP infusion and investigator’s assessment of the time of onset ≠ “Before infusion”
- TEAE = “No” otherwise
- If the date of AE onset is a partial date and the investigator’s assessment of the time of onset is not missing: TEAE = “Yes” if investigator’s assessment of the time of onset “During infusion”, “≤72h” or “>72h”
- If the date of AE onset is a partial date and the investigator’s assessment of the time of onset is missing:
 - TEAE = “Yes” if last possible date in the period defined by the partial date ≥ start date of first IMP infusion / “No” if the last possible date in the period defined by the partial date < start date of first IMP infusion
- TEAE = “Yes” otherwise

Temporally associated adverse events (TAAEs)

TAAE will be defined according to the item “Schedule” collected in the eCRF. They will include all adverse events with Schedule “During infusion”, “Within 72 hours after the end of the infusion”. If Schedule is missing then the event will be classified as TEAE by default.

Other significant AEs

Other Significant AEs are based on the definition of relevant AESIs (Adverse Events of Special Interest) for I10E. They are defined as standardized MedDRA queries (SMQs) of interest on the narrow scope, these are:

- Anaphylactic reaction (SMQ) [20000021] narrow scope
- Anaphylactic/anaphylactoid shock conditions (SMQ) [20000071] narrow scope
- Noninfectious meningitis (SMQ) [20000134] narrow scope
- Embolic and thrombotic events, vessel type unspecified and mixed arterial and venous (SMQ) [20000083] narrow scope
- Acute renal failure (SMQ) [20000003] narrow scope
- Hemolytic disorders (SMQ) [20000019] narrow scope
- Eosinophilic pneumonia (SMQ) [20000157] narrow scope
- Interstitial lung disease (SMQ) [20000042] narrow scope

Pre-treatment Adverse Events

Pre-treatment AEs will be listed for all enrolled patients.

Summary of treatment Emergent Adverse Events (TEAE)

A summary of the total number of TEAEs, and number and percentage of patients with at least one TEAE will be presented. This summary will include the number and percentage of patients having at least one TEAE as well as the absolute number of TEAEs in each AE category:

- TEAEs
- Serious TEAEs by seriousness criterion

- Drug-related TEAEs
- TAAEs
- TEAEs by severity (Mild / Moderate / Severe)

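### The stop-time rule for onset of drug-related AEs does not work for an AE that starts during an infusion, and SAP 4.7.2 and 5.7.2 can give different values for the same event

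*SAP*

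**What the plan says.** Protocol 12.10.1 asks for the interval in general terms: "the time between the last administration of study drug and the onset of the TEAE will be calculated". It names neither a start nor a stop time.

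SAP 4.7.2 is more specific. For drug-related AEs it summarises "The time between the stop time of the last administration of IMP (before the onset of event) to the onset of the drug-related AEs", in days, with the individual AE as the unit of analysis, and refers to SAP 5.7.2 for the calculation. The same section puts the elapsed time into the listings of serious TEAEs, drug-related AEs, AEs leading to dose changes or discontinuation, and other significant TEAEs. There it is described as the time "between the stop time of the last administration to the onset of the event", without the qualifier about preceding onset.

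SAP 5.7.2 introduces its formula with "The time to onset of an AE since the previous infusion will be calculated as". The calculation is AE start date minus "Date of previous IMP infusion" plus 1. It uses calendar dates and no clock times.

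AEs that start during an infusion are an expected category. On TAAEs, SAP 4.7.2 says "They will include all adverse events with Schedule" equal to during infusion or within 72 hours after its end. Neither 4.7.2 nor 5.7.2 says how time to onset is derived for the during-infusion group.

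**The concern.** An interval measured from the end of an infusion has no natural value for an event that begins before that end. The plan expects such events: Protocol 9.3 allows the infusion to be slowed or stopped for an AE, and Protocol 9.4 requires it to be stopped for allergic or anaphylactic-type reactions. When the reaction causes the stop, the stop time necessarily falls after onset. The SAP listing of AEs leading to dose changes, whose action-taken categories in 4.7.2 include interruption and a reduced flow rate, must carry this same elapsed time.

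Two programmers could each follow the SAP and enter about three weeks, about one day, 1, a negative number or a missing value for comparable events. The onset-time table could then mix intervals taken from different infusions, and a listing could show a long interval beside a Schedule entry of during infusion. Safety is the trial's secondary objective and the protocol requires this interval, so its definition should cover the case.

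**Working it through.** The plan states no figure for this variable, so there is none to reproduce. The check applies the written rules to an AE that starts during an infusion.

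**Inputs**
- Interval between courses: 21 days, window 14 to 28 (Protocol 3.1.4; SAP 4.5.1). I count it from day 1 to day 1, as SAP 4.6.2 does when it defines a shortened interval.
- Course length: course 1, 2 to 5 days; the 7 later courses, 1 to 2 days each (Protocol 3.1.4). The SAP 4.5.1 compliance rule accepts 1 to 3 days for later courses; the two texts differ, and both are carried through below.
- Assumption: one infusion per day, on consecutive days within a course.

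**Step 1: literal stop-time rule (SAP 4.7.2).** The reference is the last infusion that had stopped before onset. On the first day of a course, elapsed days = interval − (length of previous course − 1).
- Course 2: 21 − (5 − 1) = 17 to 21 − (2 − 1) = 20 days.
- Courses 3 to 8: 21 − (2 − 1) = 20 to 21 − (1 − 1) = 21 days (19 if the previous course took 3 days).
- Extremes across the window: 14 − (5 − 1) = 10 days and 28 − (1 − 1) = 28 days.
- Later day of a multi-day course: the previous infusion ended the day before, so about 1 day.
- First infusion of the study: no earlier infusion, so no value. Such an AE is still a TEAE, because SAP 4.7.2 counts onset from the start of the first infusion.

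**Step 2: date formula (SAP 5.7.2) with the same earlier infusion.** Adding 1 gives 18 to 21 for course 2, 21 to 22 for courses 3 to 8 (from 20 with 3-day courses), 2 on a later day of a course, and no value at the first infusion.

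**Step 3: the running infusion as reference.** Onset minus stop time is negative, because the stop comes later. The date formula gives 0 + 1 = 1 on every infusion day, including the first.

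**Step 4: how many infusion days are exposed.** A patient with all 8 courses has between 2 + 7 × 1 = 9 and 5 + 7 × 2 = 19 infusion days (5 + 7 × 3 = 26 under the SAP's 3 days). One has no earlier infusion and 7 refer back about three weeks: 7/9 = 78%, 7/19 = 37%, 7/26 = 27%. The rest refer to the day before. These are shares of infusion days, not of AEs.

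**Step 5: illustration for the summary table.** The documents give no share of drug-related AEs that start during an infusion. Assume a fraction f starts on a first infusion day of courses 2 to 8 (21 days as written, 0 if tied to the running infusion), and that the rest start 1 day after stop.
- Mean as written = 21f + (1 − f); mean if tied to the running infusion = 1 − f.
- SD as written = 20 × √(f(1 − f)); otherwise 1 × √(f(1 − f)).

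| f | Mean, as written | Mean, running infusion | SD, as written | SD, running infusion | Median, both | Upper quartile, as written |
|---|---|---|---|---|---|---|
| 10% | 3.0 | 0.9 | 6.0 | 0.3 | 1 | 1 |
| 20% | 5.0 | 0.8 | 8.0 | 0.4 | 1 | 1 |
| 30% | 7.0 | 0.7 | 9.2 | 0.5 | 1 | 21 |

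The maximum is 21 as written and 1 otherwise. The added day in 5.7.2 would raise every entry for location by 1 and leave the differences unchanged.

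**The case against.** The best reply is that the SAP need not be read this way. In 4.7.2 the phrase about preceding onset can qualify the administration rather than its stop, and an infusion in progress has begun before onset. Protocol 12.10.1 names no stop time. The operative formula in 5.7.2 works on dates, and at date level a same-day infusion has to be usable as reference; otherwise an AE hours after an infusion would also be sent back to an earlier one. On that reading every during-infusion AE gets 1 day, with nothing missing and nothing negative.

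This shows that a value of about 21 days is not inevitable. It does not show that the rule is sound. SAP 4.7.2 names the stop time twice, and with the running infusion that interval is negative. The wording of 5.7.2 speaks of the previous infusion and leaves the earlier one open. Nothing in either document says which reading governs.

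The other limits stand. The three-week gap applies only to first infusion days of courses 2 to 8. The fractions in the illustration are assumptions, and SAP 3.1 also reports the median and quartiles. A clock-time rule also needs a fallback, because SAP 4.7.2 itself provides for unknown onset times and partial dates.

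**Conclusion.** The concern holds as a defect in a derivation rule. For an AE that starts during an infusion, the stop-time rule refers literally to an earlier infusion (nominally 17 to 21 days back on first infusion days of courses 2 to 8, 10 to 28 across the window, usually about 1 day back on later days of a course), has no value at the first infusion, or turns negative. The date formula can return 1 for the same event. These figures rest on day-1-to-day-1 intervals and consecutive infusion days.

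A reader might infer that every during-infusion reaction will be reported about three weeks late, or that I10E reactions will look late and weakly linked to dosing. The documents do not support either. The first ignores later infusion days and the same-day reading of the formula. The second ignores outputs that do not use this variable: TAAE status comes from the Schedule item, TAAEs have their own summaries, relatedness is recorded for each AE, and drug-related TEAE rates are given by course.

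What is affected is one descriptive table, mainly its mean, SD and maximum, and the elapsed-time entry in the AE listings. TEAE and TAAE counts, relatedness and the efficacy analyses do not change. It is worth correcting, but no conclusion on efficacy depends on it.

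**What to change.** In SAP 4.7.2 and 5.7.2, define the reference as the most recent infusion whose start is at or before AE onset. Then:
- Show AEs with Schedule during infusion, or with onset before that infusion's stop, as a separate category.
- Report time from stop only for AEs that start after the stop.
- When the onset time is missing, use the Schedule item and the date of the same-day infusion.
- Apply the same rule, in the same words, to the listings.

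The cost is a wording change in two SAP sections and one revised derivation with its fallback. No new data are needed: the SAP already relies on infusion start and stop times, AE onset date-times and the Schedule item. Trial conduct is unaffected.
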